Molar Incisor Hypomineralization (MIH) is a systemic origin, qualitative developmental defect of enamel affecting one to four first permanent molars and frequently involving incisors (Weerheijm, 2001). Lesion presented as well-demarcated discolouration of the enamel, or enamel destruction due to breakdown or dental caries with a global prevalence was estimated around 14.2% (Schwendicke F et al, 2018). MIH teeth presented with various clinical problem including increase susceptibility of caries and post eruptive breakdown, inferior bonding to composite restoration, recurrent restorative failure, hypersensitivity, and difficulty to achieve anaesthesia. Extraction of the MIH affected first permanent molar is an option and require comprehensive evaluation and 'ideal' time. Currently, acceptance to invasive restorative treatment and extraction is a significant challenge in children. Hence, a less-invasive treatment using glass ionomer cement (GIC) with remineralisation and desensitising agents that comply with principle of Minimal Intervention Dentistry (MID) has gained attention as interim therapeutic restoration in moderate to severe MIH affected tooth to prevent progression of disease. Silver Diamine is a high concentration topical fluoride agent has shown superior performance for remineralization and caries arrest (Gao et al., 2016). Papain based gel is a chemomechanical caries removal and deproteinizing agent assist to remove debris and protein without the need of rotary instrument(Deng et a., 2018). There is a paucity in the published literature regarding the effect of SDF and papain-based gel on MIH-affected teeth. To date, no study has been done to evaluate the clinical outcome of MIH-affected molars treated with papain-based gel as deproteinising agent and SDF followed by interim therapeutic restoration with GIC. It is hoped that findings obtained from this study will give new insight into managing MIH-affected molars in children

Objective:

The aim of the study is to determine the clinical outcome of additional SDF with and without papain-based gel on MIH molars versus HVGIC alone as interim therapeutic restoration at 6 and 12 months. Specifically, the objective of this study is

1. To determine and compare the clinical outcome determine as success and failure of treatment related to pulpal health, structural integrity and hypersensitivity on MIH molars treated with GIC alone or with or without the use of SDF and papain-based gel at 6 and 12 months

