Sample size: The sample size is calculated based on Grossi et al., who reported that the clinical success of GIC (Equia Forte) restoration using ART technique in MIH affected permanent molars was 98.3% (Grossi et al., 2018). Since there was no literature reporting on the clinical success of Silver Diamine Fluoride and papain-based gel on MIH-affected molars, the success rate was assumed to be 50%. With an estimated error of 5% and power of 90%, the minimum estimated sample size was calculated to be 14 teeth per intervention group. The sample size calculation will be performed using G-power 3.1 software that calculated the power and sample size for tests by comparing two independent binomial populations with probabilities π_1 and π_2 , respectively. Pearson chi-square test was used to test the association of two binary variables (two groups and two outcomes). An additional 50% was added to compensate for the possibility of high dropout or recall failure. Hence, the number was increased to 21 teeth per group for a total of 63 teeth. The high percentage of dropout rate in this study is decided to accommodate a high need of retreatment of GIC restoration based on few published literature (Al Muallem et al., 2018; Linner et al., 2020). Besides, the high dropout rate may also be related to the higher chance of the affected molar to be extracted following advice by an orthodontist during the review phase.

Data Management and Analysis:

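### Sample size: GIC success is set at 98.3% while a high need for GIC retreatment is expected and booked as dropout; if re-treated teeth count as failures, 90% power is not assured

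*Combined protocol and SAP*

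**What the plan says.** The Sample size section takes its control rate from one cited study, in which "the clinical success of GIC (Equia Forte) restoration using ART technique in MIH affected permanent molars was 98.3" per cent. For the SDF and papain groups, having found no literature, it says "the success rate was assumed to be 50" per cent. The test is a two-group Pearson chi-square: "With an estimated error of 5% and power of 90" per cent, "the minimum estimated sample size was calculated to be 14 teeth per intervention group".

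The section then adds 50% for dropout or recall failure, giving 21 teeth per group and 63 in total. It gives two reasons for so large an addition. One is "to accommodate a high need of retreatment of GIC restoration", for which it cites other literature. The other is possible extraction on orthodontic advice.

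Four other places bear on this:
- The Objective defines the outcome as "success and failure of treatment related to pulpal health, structural integrity and hypersensitivity".
- Table 1 (under Observation) counts new caries or enamel breakdown at the restoration margin as a minor failure. It lists neither retreatment nor loss of the restoration.
- Under Intervention, all three groups are restored with HVGIC.
- Data Management and Analysis makes intention-to-treat on every randomised tooth primary, with per-protocol as a sensitivity analysis. It gives no rule for the value assigned to a re-treated tooth.

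**The concern.** One paragraph makes two statements about GIC restorations in MIH molars that pull against each other. The power calculation allows 1.7% failures with GIC. The dropout allowance expects retreatment of GIC to be common.

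Retreatment is not like a missed recall. It bears on structural integrity, which the Objective makes part of the outcome, and many re-treated teeth would probably show marginal breakdown or caries. Booking such teeth as losses removes probable failures from the basis of the power calculation. The 90% then describes only teeth that did not need retreatment, a subset selected on something close to the outcome. The primary analysis set is different: it keeps every randomised tooth.

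At stake is whether 90% describes the analysis the plan calls primary, and whether the team will know how to score these teeth when they appear.

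**Working it through.** **Inputs.** From the Sample size section: GIC success 0.983, comparator success 0.50, error 5% (sidedness not stated; two-sided used here), power 90%, 14 teeth per group raised to 21. Assumed, because the documents give no figure: r, the share of teeth re-treated.

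**1. Reproducing the plan's figures.** For 0.983 against 0.50 at 90% power, the normal-approximation formula without continuity correction gives 16 per group two-sided and 13 one-sided. Exact enumeration of the uncorrected two-sided Pearson test first reaches 90% at 13. The stated 14 lies within this range. Power at 14 teeth is 87.5% by normal approximation and 92.7% by exact enumeration. The addition is 14 × 1.5 = 21, which tolerates a loss of 7/21, or one third.

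**2. Retreatment as dropout (the plan's accounting).** If 7 of 21 teeth are lost, 14 remain and power is again 87.5% to 92.7%. On this accounting the stated 90% roughly stands.

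**3. Retreatment as failure (teeth kept in the analysis).** GIC success becomes 0.983 × (1 − r). The comparator is handled in two ways: lowered in the same proportion, 0.50 × (1 − r), because its teeth also receive HVGIC; or held at 0.50. Power is the sum of the binomial probabilities of all result pairs for which the two-sided Pearson test is significant at 5%.

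| r | GIC success | Comparator if lowered | Power, 21 per arm, both lowered | Power, 21 per arm, comparator 50% |
|---|---|---|---|---|
| 0 | 0.983 | 0.500 | 99% | 99% |
| 5% | 0.934 | 0.475 | 95% | 93% |
| 10% | 0.885 | 0.450 | 90% (89.6%) | 82% |
| 20% | 0.786 | 0.400 | 74% | 51% |
| 1/3 | 0.655 | 0.333 | 55% | 17% |

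Example at r = 20%: 0.983 × 0.80 = 0.786 and 0.50 × 0.80 = 0.400.

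If seven other teeth per arm were also lost, leaving 14 analysed, exact power would be:
- both lowered: 73% at r = 10%, 55% at 20%, 37% at one third;
- comparator 50%: 64%, 35% and 12%.

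**4. Lowest GIC success that keeps 90% power (comparator 50%, exact test).** About 92% with 21 teeth (0.918) and just over 97% with 14 teeth (0.973). By normal approximation the 21-tooth figure is 93%.

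**5. Power by GIC success rate (comparator 50%, exact test).**

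| GIC success | 14 per arm | 21 per arm |
|---|---|---|
| 98.3% | 93% | 99% |
| 95% | 84% | 96% |
| 90% | 69% | 86% |
| 80% | 39% | 56% |

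**The case against.** The strongest reply is that the plan is consistent on its own terms. It treats retreatment as dropout, allows for one third of teeth to go, and still has 14 per group with about 90% power. Table 1 does not list retreatment as a failure, and restorative quality is named separately from clinical outcome in the analysis section. The 98.3% and the retreatment expectation come from different cited sources, which may differ in product, technique, follow-up and definition of success.

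Much of this stands. A reader might infer that 90% power holds only if almost no GIC tooth is re-treated, or that the plan's own expectation rules out 98.3%. The documents support neither. The first needs the premise that retreatment means failure, which Table 1 does not state. Even on that premise, with 21 teeth analysed, power is 93% to 95% at 5% retreatment and 89.6% at 10% if both compared arms are affected equally. The second would need a retreatment rate, and none is given. The 12% and 17% figures are also the harshest case: they hold the comparator at 50% although its teeth receive the same restorative material.

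The reply does not settle how a tooth can be a dropout for power and remain in the primary intention-to-treat analysis with no stated score. Recall failure and orthodontic extraction are ordinary grounds for an allowance. Retreatment differs because it bears on the endpoint.

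**Conclusion.** The concern holds in conditional form. The plan expects substantial GIC retreatment, counts it as loss, and does not say how such teeth enter an analysis that keeps them. If they are failures, the stated 90% is not assured. With all 21 teeth per arm analysed, it survives about 10% retreatment when both compared arms are affected equally, and about 5% but not 10% when only the GIC arm is. At 20%, power is 74% or 51%.

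These figures rest on three assumptions: a re-treated tooth is a failure, r is chosen for illustration, and the test is the two-sided uncorrected Pearson test. Nothing here shows that the true GIC success rate differs from 98.3%, or that 63 teeth are too few. The literature cited in the plan was not examined.

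**What to change.** Keep 63 teeth and make three changes of wording.

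1. In Sample size, remove retreatment from the reasons for the dropout allowance. Recall failure and orthodontic extraction can stay.
2. In the outcome definition (Table 1) and the intention-to-treat description, state that a tooth whose study restoration is re-treated stays in the analysis and is counted as a treatment failure, not as missing.
3. Replace the single 90% with power over a range of GIC success rates, for example 98%, 92%, 90% and 80%, and say which support 90%. With 21 teeth analysed and the comparator at 50%, rates of about 92% and above do; with 14 analysed, only rates just over 97% and above do.

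No extra teeth, visits or tests are needed. The downside is a less favourable stated power.

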Methodology:

Study Design: This study is a single centre, three arms, parallel randomised controlled trial (RCT) on MIH molars in children aged 5 to 15-year-old presented with at least one molar tooth diagnosed as MIH. RCT was opted as it allows comparison of data with the conventional management using GIC which is a common interim therapeutic restorative material of choice.

Research Subject and Participant: MIH screening and diagnosis of the first permanent molar will be done using the European Academy of Paediatric Dentist (EAPD) MIH index by Ghanim et al., 2015, ICDAS caries assessment, clinical assessment, and radiographic evaluation. The inclusion criteria of the participant and molar include.

1. Children aged 5 – 15 years old
2. Healthy with no medical problem
3. Subject presented with at least one MIH FPM with:
 - a. Post eruptive breakdown (PEB)
 - b. Unsatisfactory atypical restoration
 - c. Atypical caries without pulp involvement

The exclusion criteria of the participant and molars include

1. Children with difficulty comprehending instruction
2. Children with inability to perform oral hygiene care independently
3. Known allergy to silver
4. Affected FPM with
 - a. Non MIH defect (Fluorosis, Amelogenesis Imperfecta)
 - b. No PEB and carious lesion
 - c. Lesion into the pulp

- d. Intact restoration
- e. Extensive coronal breakdown requiring extraction

Upon obtained of informed consent, based on the tooth as the unit, it will then be randomised (1:1:1 via blocks) to either intervention arms by an independent collaborator based on the allocation sequence. The collaborator will not be involved in the study and was responsible for keeping the randomisation list. The randomisation allocation sequence will be generated using computer software.

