Intervention: Intervention will be carried out by single investigator who is not involved in assignment of the samples. Group 1 will receive High Viscous Glass Ionomer Cement (HVGIC) restoration; Group 2 will be treated with 38% SDF (RivaStar®) and restored with HVGIC, and Group 3 will receive papain-based gel, Papacarie Duo™ followed by 38% SDF application and HVGIC restoration. In this study, 38% SDF by the RivaStar was the only SDF available and marketed in Malaysia. It is approved by the Malaysia Device Authority and U.S Food and Drug Administration (FDA) in 2014. In addition, the papain base gel (Papacarie Duo™) was obtained from the manufacturer and has been used in many clinical studies as chemomechanical caries removal agent as well as deproteinizing agent to improve adhesion of composite (Goyal et al., 2015, Pithon et al., 2016, Bottega et al. 2018)

Observation: At 6- and 12-months follow-ups, the findings for this study will be assessed by a blinded assessor who was not involved in recruitment and intervention. The clinical parameters recorded include presence of pain, swelling, tenderness, abscess, enamel breakdown, restoration quality, presence of caries associated with the tooth and Schiff Cold Air Sensitivity Scale (SCASS). This clinical outcome of the molar; success or failure will then be determined based on the clinical parameters.

Table 1: Description of the clinical outcome

Outcome	Description
Success	
 • Absence of pain related to the treated tooth • Absence of tenderness to percussion • No evidence of swelling or presence of a sinus tract • Absence of enamel breakdown and caries along margin of restoration • No hypersensitivity (SCASS 0 or 1)
Major failure	
 • Presence of spontaneous throbbing or persistent pain • Presence of tenderness to percussion • Evidence of swelling and sinus
Minor failure	
 • Presence of new carious lesion or enamel breakdown at the margin of restoration • Presence of hypersensitivity (SCASS 2 or 3)

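### The plan gives no outcome to molars extracted or restorations retreated during review, so failures can be lost as missing data despite the stated ITT analysis

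*Combined protocol and SAP*

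**What the plan says.** Four places in the combined protocol and SAP bear on this.

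- **Sample size.** The minimum of 14 teeth per group is increased by half, to 21 per group and 63 in all, to cover dropout. Two reasons are offered for so large an allowance: GIC restorations often need retreatment, and there is a "higher chance of the affected molar to be extracted following advice by an orthodontist during the review phase".
- **Table 1 (Methodology, Observation).** Outcomes are success, major failure and minor failure. Success requires, among other things, "Absence of enamel breakdown and caries along margin of restoration"; its converse is a minor failure. Extraction and retreatment appear under no category.
- **Exclusion criterion 4e (Methodology).** A first permanent molar is not eligible if it has "Extensive coronal breakdown requiring extraction".
- **Data Management and Analysis.** The primary analysis is ITT on all randomised teeth. A per-protocol analysis is the sensitivity analysis for missing values. The section gives no imputation rule and no rule for a tooth that cannot be examined at 6 or 12 months.

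**The concern.** The plan foresees two events after treatment, retreatment and extraction, and places both in its dropout allowance. Neither is clearly unrelated to the outcome. Retreatment is a direct sign that the restoration has failed. Extraction may follow breakdown of the tooth: criterion 4e shows that the protocol recognises breakdown as a reason for extraction, although only at entry.

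If such teeth are handled as missing, the teeth lost are disproportionately failures and the observed success rate is too high. If the losses differ between arms, the comparison is biased as well. That bias can hide a real difference or create a false one. With 21 teeth per arm, a few teeth are enough to matter.

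**Working it through.** **1. The plan's own figures.** Inputs from the Sample size section: success 98.3% (control) and 50% (assumed for the new treatments), error 5%, power 90%, Pearson chi-square for two groups. Sidedness is not stated; two-sided is assumed.

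n = [z₀.₉₇₅ √(2p̄(1−p̄)) + z₀.₉₀ √(p₁(1−p₁) + p₂(1−p₂))]² / (p₁−p₂)²

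Here p̄ = (0.983 + 0.5)/2 = 0.7415, so n = [1.960 × 0.619 + 1.282 × 0.516]² / 0.483² ≈ 15.1, rounded up to 16. Exact enumeration of the Pearson test gives 90.1% power at 13 per group and 92.7% at 14. The stated 14 is therefore reproduced within 2 teeth. Then 14 × 1.5 = 21 and 21 × 3 = 63. The sample-size arithmetic is not in dispute. What matters here is that the plan tolerates the loss of 7 of 21 teeth per arm, which is 33.3%.

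**2. What the documents assign to each event.**

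| Event during review | Sample size | Table 1 | Analysis section |
|---|---|---|---|
| Restoration retreated | reason for dropout allowance | no entry | in the ITT set, no outcome rule |
| Molar extracted | reason for dropout allowance | no entry | in the ITT set, no outcome rule |
| Marginal breakdown or new caries, tooth still present | not mentioned | minor failure | analysed as a failure |

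The same deterioration is a failure if the tooth is examined at the visit, and has no defined outcome if the tooth was extracted beforehand.

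**3. Size in one arm.** No extraction rate is given, so this is an assumption: 21 teeth, of which 15 succeed, 3 fail and 3 are extracted. Let k of the 3 extracted teeth have failed, with the others sound and properly missing. Dropping all three gives 15/18 = 83.3%. The rate that counts the k failures is 15/(18 + k).

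| k | Rate counting failures | Overstatement if all 3 are dropped |
|---|---|---|
| 0 | 15/18 = 83.3% | 0 points |
| 1 | 15/19 = 78.9% | 4.4 points |
| 2 | 15/20 = 75.0% | 8.3 points |
| 3 | 15/21 = 71.4% | 11.9 points |

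**4. Limits set by the plan's allowance.** Suppose 7 of 21 teeth are lost. If half of the remaining 14 succeed, the arm's rate is 7/14 = 50.0% with losses dropped, 7/21 = 33.3% with all losses as failures, and 14/21 = 66.7% with all as successes. With 98.3% success among the 14, the three rates are 98.3%, 65.5% and 98.9%.

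**5. Direction.** Both cases are assumed.

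- *False difference.* Two arms each have 14 successes and 7 failures. If all 7 failures in one arm are extracted and dropped, the comparison is 14/14 against 14/21: Pearson p = 0.016, Fisher p = 0.027. Counted as failures, it is 14/21 against 14/21, p = 1.0. If 5 of the 7 are dropped, it is 14/16 (87.5%) against 14/21 (66.7%), Pearson p = 0.14.
- *Hidden difference.* True rates are 15/21 = 71.4% and 18/21 = 85.7%, a gap of 14.3 points. If 3 failed teeth are dropped from the first arm only, it shows 15/18 = 83.3% and the gap falls to 2.4 points.

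**The case against.** The best reply is that the analysis section already answers the point: ITT on all randomised teeth keeps extracted teeth in the denominator. That is true of the analysis set. However, ITT does not supply an outcome for a tooth that can no longer be examined, and the plan does not supply one elsewhere. The per-protocol check does not help. The plan does not define its population, but on the usual definition it would omit the same teeth.

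A second reply is that the extractions named are orthodontic. This stands in part. The Rationale says extraction needs full evaluation and suitable timing, which fits reasons other than restoration failure. The fix has to leave room for sound teeth removed on those grounds.

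A reader might infer that the protocol itself links extraction during review to coronal breakdown. It does not. Criterion 4e applies at entry, and it removes the teeth most obviously heading for extraction. It makes outcome-related extraction plausible without showing that it will happen. A reader might also infer that the plan has decided to drop extracted teeth. The sentence in question is a hedged remark about recruitment numbers, not an analysis rule. The defect is the absence of a rule.

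The retreatment route is less exposed to these replies, because it needs no inference from criterion 4e.

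**Conclusion.** The point holds as a gap in outcome definition and missing-data handling. The plan expects retreatment and extraction often enough to help justify a 50% uplift, yet it leaves both without an outcome, and its only missing-value check is unlikely to recover them. A team following the plan as written could lose failures from the analysis.

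The size cannot be fixed from the documents. The 12-point figure is the top of an assumed range of 0 to 12 points, reached only if all three extracted teeth had failed and all were dropped; it is not an expected bias. The sign of any bias in the comparison is also open. The missing rule is certain, and the share of extractions related to outcome is unknown. The change should be made, with medium confidence in its practical effect.

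**What to change.** - **Record the reason** for every extraction or retreatment, and have the blinded assessor classify it.
- **Add an outcome rule to Table 1 for the ITT analysis.** An extracted or retreated tooth is a failure if any Table 1 failure criterion was present at a post-treatment assessment, or if it was extracted or retreated because of the condition of the tooth or restoration. The pre-treatment baseline must never be used for this. Breakdown is among the entry conditions, and pain or sensitivity may predate treatment, so baseline status would score teeth as failures whatever the treatment did.
- **Limit what is missing.** Among extracted teeth, treat as missing only a sound tooth removed for purely orthodontic reasons.
- **Add a sensitivity analysis** counting every extracted tooth as a failure, alongside the per-protocol analysis.

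The cost is one case-report field, a line in the outcome definition and one extra table. The downside is that success may be slightly understated if reasons are misrecorded. The change concerns how outcomes are classified, not when a tooth should be extracted or retreated.

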Data obtained will be entered and analysed using Statistical Package for the Social Sciences (SPSS) version 26.0 software. The continuous data will be checked for normality of distribution and reported accordingly. Categorical data in this study are the clinical parameters, clinical outcome, and restorative quality. Descriptive statistics of frequencies and percentages will be presented for categorical data. The primary data analysis will be done using Intention-to-treat (ITT) analysis involving all the samples recruited and randomised. The Per Protocol (PP) analysis will be done to compare the difference between treatment effects as a sensitive analysis of missing value. Comparison of categorical outcomes will be assessed using Chi-square goodness of fit test and Friedman Two-way Analysis of Variance (ANOVA) by Ranks test. Association studies such as factors affecting the outcome will be further evaluated using the Binary Logistic Regression. In all analyses, the level of significance is set at $p<0.05$. The power of the study will be calculated using G*Power Version 3.1.9.4 using the Post Hoc test of Goodness-of-Fit.

Ethical Consideration:

This study has already received approval from the Medical Ethics Committees, Faculty of Dentistry, University of Malaya (CD1912/0061/20155(P)). Patient Information Sheet (PIS) will be disseminated to parents and participated children before consenting. Written informed and verbal consent from parents and, where appropriate, the children, were obtained before intervention. Participation is based on a voluntary basis and they may decide to leave at any time of the study.

Reference:

1. Almualllem, Z. & Busutil-Naudi, A. 2018. Molar incisor hypomineralisation (MIH) – an overview. *British Dental Journal*, 225, 601-609.
4. Gao, S. S., Zhang, S., Mei, M. L., Lo, E. C.-M. & Chu, C.-H. 2016. Caries remineralisation and arresting effect in children by professionally applied fluoride treatment – a systematic review. *BMC Oral Health*, 16.

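### The per-protocol analysis is the only planned check on missing values, but it does not vary what is assumed about unseen teeth, and the ITT analysis has no score for retreated, extracted or unseen teeth

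*Combined protocol and SAP*

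**What the plan says.** Data Management and Analysis makes the primary analysis an "Intention-to-treat (ITT) analysis involving all the samples recruited and randomised". The next sentence gives PP its purpose: it "will be done to compare the difference between treatment effects as a sensitive analysis of missing value". The document mentions no imputation, no rule for scoring a missing outcome, no best- or worst-case bounds and no tipping-point analysis. It does not define the PP set.

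The Sample size section adds 50% to the calculated 14 teeth per group "to compensate for the possibility of high dropout or recall failure", so that "the number was increased to 21 teeth per group for a total of 63 teeth". It gives two reasons for the margin. One is to "accommodate a high need of retreatment of GIC restoration". The other is that molars may be extracted on orthodontic advice during review.

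Table 1 defines success, major failure and minor failure from clinical findings. It has no category for a tooth that was retreated, extracted or not seen.

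**The concern.** A sensitivity analysis for missing values has to change the assumption about the outcomes nobody saw and show whether the conclusion survives. PP in its usual meaning leaves those teeth out and gives a single result. It also removes teeth with protocol deviations, so a difference between ITT and PP cannot be put down to missing data alone.

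What the comparison shows depends on how ITT treats a tooth without an outcome, and the plan does not say. A chi-square test or logistic regression run without a scoring rule drops such teeth. ITT and PP would then rest on nearly the same data, and agreement between them would say nothing about the missing outcomes.

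The plan's own reasons for loss make this more than a formality. Retreatment of a GIC restoration plausibly follows its failure. All three arms receive HVGIC, but the trial asks whether SDF and papain gel change failure, so failure-related loss could differ between arms. Success rates could then be too high, and unequally so.

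**Working it through.** **Inputs from the documents.** Sample size: 14 teeth per group, raised by 50% to 21; success 98.3% with GIC and 50% assumed for the new treatments; Pearson chi-square test. Intervention: three arms, all restored with HVGIC. Observation: visits at 6 and 12 months.

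**The plan's own figures.** For 98.3% versus 50% at two-sided 5% and 90% power, the usual formulas without continuity correction give 13 (unpooled variance) to 16 (pooled variance) per group. The exact power of the uncorrected Pearson test is 90.1% at 13 per group and 92.7% at 14. The stated 14 is therefore reasonable. The margin is 14 × 1.5 = 21, so the loss covered is (21 − 14)/21 = 7/21 = 33.3% per arm.

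**How far 7 missing teeth per arm can move a result.** With s successes among 14 observed teeth, the arm's rate over 21 teeth lies between s/21 and (s + 7)/21, a width of 7/21 = 33 points. The difference between two arms therefore has a range of 67 points, 33 either side of its midpoint.

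**Illustration A (assumed: 12/14 observed successes in both arms).**

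| Assumption about the 7 missing per arm | Rates | Difference | Pearson p | Fisher p |
|---|---|---|---|---|
| Left out (usual PP) | 12/14 v 12/14 | 0 | 1.0 | 1.0 |
| All failures, both arms | 12/21 v 12/21 | 0 | 1.0 | 1.0 |
| Failures in one arm, successes in the other | 12/21 v 19/21 | 33 points | 0.014 | 0.032 |

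**Illustration B (assumed: the plan's own rates among the observed teeth, 14/14 control and 7/14 experimental).**

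| Assumption about the 7 missing per arm | Rates | Difference | Pearson p | Fisher p |
|---|---|---|---|---|
| Left out (usual PP) | 14/14 v 7/14 | 50 points | 0.002 | 0.006 |
| All failures, both arms | 14/21 v 7/21 | 33 points | 0.031 | 0.063 |
| Against the difference | 14/21 v 14/21 | 0 | 1.0 | 1.0 |

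Even the very large difference the trial was sized for can vanish at the bound. PP gives only the first row of each table.

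**Illustration C (assumed: one arm of 21 with 13 successes and 8 failures, 6 of the failures retreated and dropped).** Teeth left: 21 − 6 = 15. Apparent success: 13/15 = 86.7%. Success with the retreated teeth scored as failures: 13/21 = 61.9%. If ITT is run on observed teeth, ITT and PP both show about 87%. If ITT scores the retreated teeth as failures, ITT shows 62% against 87% for PP, and the gap is visible. The unstated ITT rule decides which of these happens.

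**The case against.** Five points on the other side deserve a fair hearing.

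- **PP may not be useless.** An ITT analysis of all randomised teeth implies that every tooth has a value. If missing were scored as failure, ITT against PP would contrast two assumptions, as Illustration C shows. This stands, so a reader who infers that PP must reproduce the bias goes too far: that holds only if ITT uses observed teeth. But the plan states no scoring rule, and the contrast would still mix missingness with adherence.
- **The plan does not forecast the loss of a third or more.** It allows for the possibility of high dropout. The arithmetic supports 33% as the allowance. Any larger figure needs the 50% to be read as a dropout rate, whereas 14 × 1.5 = 21 shows how it was applied.
- **The plan does not say that retreated teeth lose their outcome.** A reader might infer that outcomes go missing because treatment failed. The Sample size section only explains a margin, and Table 1 already counts new caries or enamel breakdown at the restoration margin as minor failure, which can be recorded at a visit before any retreatment. Failure-related loss is plausible, not stated. The gap is retreatment between visits and whether a 6-month failure counts at 12 months.
- **The p of 0.014 comes from a chosen extreme.** It assigns opposite outcomes to the two arms, and Fisher's test gives 0.032. Scoring missing as failure in both arms leaves p at 1.0. The bounds are limits, not predictions.
- **Arm-specific multiple imputation would be a poor remedy.** At 98.3% success, 14 observed control teeth have 14 × 0.017 = 0.24 expected failures and a 0.983^14 = 79% chance of none, so there would usually be nothing to model. Teeth lost before 6 months have no interim result either. This stands and shapes the fix.

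**Conclusion.** The concern holds in this form: PP is inadequate as the only check on missing values, and the primary ITT analysis lacks a score for retreated, extracted and unseen teeth. This is more than missing detail, because a named method has been given a task it is not suited to and a better one is cheap.

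With the loss the sample size allows for, each arm's success rate is undetermined by up to 33 points, and the difference between two arms can range over 67 points. In an arm where retreated failures drop out, success could read 87% instead of 62%.

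These sizes rest on assumptions: that the full 7 of 21 per arm are lost, that the observed counts are as in the illustrations (they are not trial data), and that PP has its usual meaning of leaving out teeth without an outcome. False reassurance from agreement between ITT and PP further requires that ITT is run on observed teeth, which the plan neither says nor excludes.

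**What to change.** Before analysis, add to Data Management and Analysis:

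1. In the ITT analysis, a tooth retreated because of failure before 12 months is scored as a failure, and a failure recorded at 6 months is carried forward to 12 months. These are scoring rules and do not affect clinical care.
2. Teeth extracted on orthodontic advice and teeth not seen are treated as missing. One simple rule for them is stated for the primary analysis, for example missing = failure in all arms, rather than multiple imputation by arm.
3. Best- and worst-case bounds and a tipping-point table by arm replace PP as the missing-data check. This also guards against the chosen primary rule being wrong.
4. The PP set is defined and PP is kept as an adherence analysis only.

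The cost is some plan wording, a few extra tables, and recording the date and reason for each retreatment, extraction or missed visit. The success rates will probably look less favourable, and missing = failure will count some teeth as failures that were not, which is why the bounds should be reported beside it.
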